The clinical study that supported clearance of K191257 and K212595 was a single arm (active treatment only), historical comparative design to demonstrate non-inferiority of the standard Erchonia red laser therapy when used in simultaneous combination with violet laser therapy compared with application of the standard Erchonia red laser therapy protocol alone in the temporary reduction of neck and shoulder pain of musculoskeletal origin. The historical comparative active data set for that clinical study used for non-inferiority analysis was the results from the Erchonia® red diode therapy only active subject group attained in the 2001 trial whose results successfully supported 510(k) clearance (K012580) of application of red laser light therapy only for the identical indication. This same historical comparative active data set will be used as the historical comparative Erchonia red laser therapy only active treatment data set for the current proposed clinical study.

SUBJECT GROUP

There will be a single subject group treated in this study. All subjects will receive the active study treatment with the blue laser therapy using the Erchonia® PPL first followed sequentially with the standard Erchonia red laser therapy (*Erchonia XLR8, FDA cleared under K211186*)

Comparative subject data for the red diode alone procedure administration will be taken from the Erchonia 2001 study whose results supported FDA market clearance for K012580.

BLINDING

As all subjects in this study will receive active treatment administrations with the Erchonia® PPL and the Erchonia XLR8, neither subjects nor investigators will be blinded. The statistician analyzing the study results will however be blinded with respect to study success analysis. The data from this combined laser therapy study and the retrospective comparative data from the 2001 red diode only study will be deidentified and presented to the study statistician as 'Group A' and 'Group B'. The statistician will not be aware of which group – A or B – contains the current combined laser therapy data and which contains the retrospective comparative red diode only data.

RANDOMIZATION

As this study is a single treatment group study, randomization to treatment group is not applicable. Therefore, this is a non-randomized trial.

SUBJECTS

Subject Sample

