Mobility in the neck/shoulder region will be measured using a universal inclinometer, as follows:

- (i) Shoulder ROM will be measured from a seated passive abduction, the relaxed position of parallel to the side of the body through full extension above the head. Maximum movement is 180 degrees.
- (ii) Neck ROM will be measured in a supine position, from forward position to face over shoulder. Maximum movement is 90 degrees.

SUBJECT SATISFACTION WITH STUDY OUTCOME

The subject is asked to rate how satisfied he or she is with any change in neck/shoulder pain following completion of the laser administration procedure with the Erchonia Lasers by using the 5-point Likert scale below to respond to the following question: "Overall, how satisfied or dissatisfied are you with any change in the pain in your neck and/or shoulder following the study treatment with the study laser devices?"

- Very Satisfied
- Somewhat Satisfied
- Neither Satisfied nor Dissatisfied
- Not Very Satisfied
- Not at All Satisfied

STUDY PROCEDURE PROTOCOL

PRE-TREATMENT ACTIVITIES

Pre-treatment activities will be performed at the study site prior to administering the sequential Erchonia® PPL blue laser therapy followed by the standard Erchonia XLR8 red laser therapy.

STUDY QUALIFICATION

SIGNING OF INFORMED CONSENT FORM

The PI will commence by presenting and reviewing in detail the items in the informed consent form with the individual and answer any questions. To proceed, the individual must willingly sign the informed consent form.

ASSIGNMENT OF SUBJECT IDENTIFICATION NUMBER

The subject is assigned a unique de-identified subject identification number based upon his or her order of entry into the study. The Subject ID number will comprise the initials of the test site Principal Investigator's first and last name followed by a single digit number that represents the test site number (e.g. test site #1 = 0, test site #2 = 1, etc.) and then a two-digit number that represents the subject's order of entry in the study.

For example, the 14th subject to be enrolled at test site #2 with Principal Investigator John Black will have a Subject ID of JB114.

STUDY QUALIFICATION EVALUATION: INCLUSION/EXCLUSION CRITERIA

INCLUSION CRITERIA

To be eligible for study participation, a subject must satisfy each of the following criteria.

1. Signed informed consent form
2. 22 years of age or older
3. Primary language is English
4. Subject presents with one or more of:

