24 HOURS AND 48 HOURS POST-TREATMENT EVALUATIONS

The subject will be required to record the following at home on the forms provided by the test site at 24 hours and again at 48 hours after completion of the treatment administration phase at the test site.

OUTCOME ASSESSMENTS

- Visual Analog Scale (VAS) Degree of Pain Rating
- Linear Range of Motion (ROM)
- Subject Satisfaction with Study Outcome Rating
- Adverse Events Evaluation

STATISTICAL ANALYSIS PLAN

Populations Examined

Two (2) subject populations will be analyzed, as applicable:

- (i) **Intent-to-Treat (ITT) Population:** All enrolled subjects regardless of whether any measures are recorded and/or treatment is administered.
- (ii) **Per-Protocol (PP) Population:** All enrolled subjects who completed the study per protocol through to the 48-hour post-treatment evaluation, excluding subjects with major protocol deviations, incompletes, etc.

Primary analysis of efficacy will be according to the intent to treat (ITT) population and the secondary supportive analysis will be according to the per protocol (PP) population. Non-inferiority will be established if both the ITT and PP analyses agree.

Handling of Missing Data

Missing data will be handled through multiple imputation analysis, a strategy to handle missing values in a clinical trial wherein each missing value is replaced with a set of plausible values that represent the uncertainty about the right value to impute. The exact method of multiple imputation analysis will be determined after study completion depending on factors such as the amount of missing data and whether it is determined that the data are missing at random (MAR) or missing not at random (MNAR).

PRIMARY EFFICACY OUTCOME MEASURE: CHANGE IN SUBJECT SELF-REPORTED VAS PAIN RATING FROM BASELINE TO STUDY ENDPOINT

The aim of this study is to determine if the treatment effect of the sequential therapy with the Erchonia® PPL blue laser therapy followed by the Erchonia® XLR8 standard red laser therapy for the active treatment group in this study is equal to or superior to that attained for the active comparative treatment group in the comparative reference study who received the standard red laser therapy alone.

Proportion of Successes

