- *Null Hypothesis:* Sequential treatment application of the Erchonia® PPL blue laser therapy followed by the standard Erchonia® red laser therapy using the XLR8 is inferior to treatment application of the Erchonia red laser therapy alone in reducing neck and shoulder nociceptive pain of musculoskeletal origin to the effect of 60% or fewer subjects attaining a 30% or greater reduction in neck and shoulder pain at study endpoint evaluation relative to baseline.

$H_0: P \leq 60\%$; where P = individual subject responder rate

- *Alternative Hypotheses:* Sequential treatment application of the Erchonia® PPL blue laser therapy followed by the standard Erchonia® red laser therapy using the XLR8 is NOT inferior to (i.e., is equivalent to or superior to) treatment application of the Erchonia red laser therapy only in reducing neck and shoulder nociceptive pain of musculoskeletal origin to the effect of greater than 60% of subjects attaining a 30% or greater reduction in neck and shoulder pain at study endpoint evaluation relative to baseline.

$H_1: P > 60\%$; where P = individual subject responder rate

Evaluation Time Point

Study endpoint evaluation was preestablished as occurring immediately (within 3 minutes) following completion of administration of the second component of the sequential study treatment with the standard Erchonia® red light laser device. Study primary success analysis is preestablished at study endpoint relative to baseline, identically to that in the 2001 reference comparative study.

Change Scores

- T-test analysis of the difference in the mean change in VAS levels from baseline to endpoint between the dual-diode and red only diode treatment administration groups. Significance levels will be considered at the $p < 0.05$ level.
- A t-test for two independent sample will be performed to evaluate the significance of the difference in the mean change in VAS pain scores from baseline to endpoint evaluation between the two study groups to evaluate for equivalency to support the support the conclusion of the proportion of successes evaluation. Significance levels will be considered at the $p < 0.05$ level.

SECONDARY EVALUATIONS

The following secondary evaluations will be performed on the per protocol study data set only. As no claims are intended to be made based on secondary measures, the findings will be presented through descriptive analysis and qualitative trending only, without evaluation for or claims of statistical significance.

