- Each subject will be made aware that his or her records will remain confidential, but that the FDA and the IRB has the right to inspect his or her records.
- Each subject will be told that his or her participation in the clinical study is voluntary, without force or influence from the investigator or sponsor.
- Each subject will be given the name and method of contacting the appropriate person(s) to answer his or her questions about the research and in the event of a research-related injury.

The informed consent form that will be used to collect the data from each subject in this clinical study can be found in **Appendix B**.

Confidentiality and Privacy

Subject confidentiality and privacy are strictly held in trust by the participating investigators, study staff, and the sponsor(s) and their interventions. Therefore, the study protocol, documentation, data, and all other information generated will be held in strict confidence. No information concerning the study, or the data, will be released to any unauthorized third party without prior written approval of the sponsor.

All research activities will be conducted in as private a setting as possible.

The study monitor, other authorized representatives of the sponsor, representatives of the IRB, or regulatory agencies may inspect all documents and records required to be maintained by the investigator for the subjects in this study. The clinical study site will permit access to such records.

Records for each subject in this clinical study will be maintained in separate files in a locked filing cabinet at the test site. The investigator at the test site will be responsible for ensuring that all records for a subject pertaining to his or her participation in the clinical study are always stored in that subject's file other than when information is being recorded on them.

The study Monitor will have access to the files for the purposes of data monitoring and auditing. Once the study is complete, copies of each of the subject case report forms will be made and supplied to the study statistician for analysis of results. The study statistician will maintain these copies in a separate clinical study file that is kept in a locked filing cabinet on their premises.

The original records will be maintained at the respective test sites upon completion of the study in their original files and stored in a locked filing cabinet.

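### The Group A/B masking of the statistician is not achieved as written, because the same statistician receives every current-study case report form while imputation and exclusion rules are still open

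*Combined protocol and SAP*

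**What the plan says.** All references are to the combined protocol and SAP.

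- **Blinding (Study Design).** Subjects and investigators are not blinded. For the analyst the section says: "The statistician analyzing the study results will however be blinded with respect to study success analysis". The current data and the 2001 red-laser data are to be de-identified and labelled Group A and Group B, and the statistician is not to know which is which.
- **Confidentiality and Privacy.** When the trial has ended, "copies of each of the subject case report forms will be made and supplied to the study statistician for analysis of results". On custody this section adds: "The study statistician will maintain these copies in a separate clinical study file", held on the statistician's own premises.
- **Handling of Missing Data.** "The exact method of multiple imputation analysis will be determined after study completion", depending on the amount of missing data and on whether it is judged missing at random or not at random. No decision-maker is named.
- **Populations Examined.** The primary ITT set is "All enrolled subjects regardless of whether any measures are recorded and/or treatment is administered". The per-protocol set drops subjects with major protocol deviations, which are not listed, and the sentence ends in an open-ended etc. Non-inferiority requires the two analyses to agree.
- **Hypotheses.** The null is P ≤ 60%, "where P = individual subject responder rate", and it concerns the current treatment.

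**The concern.** Two sections give the same role incompatible access. A statistician who holds the current study's completed forms can match a few VAS values to one of the coded groups, and the code is then broken.

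The A/B masking is the only blinding in an otherwise open study with a historical control, and a reader of the submission may give it weight. Behind it, two analysis decisions that can affect the primary conclusion remain open: how missing endpoints are imputed, and who leaves the per-protocol set. If the masking fails, nothing in the plan prevents either decision from being made by someone who has seen outcomes and knows which group is current.

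**Working it through.** **1. Can the statistician identify the groups?**

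- *Forms.* Those supplied are current-study forms, and every subject's form is copied. They hold the subject-level values that also form one of the two coded groups, so matching identifies that group. Appendix C is not shown, but matching on values does not depend on how the forms are worded.
- *Printed results.* The section on supporting Erchonia clinical data gives 65.1% responders in the 2001 active group, and mean VAS falling from 60.21 to 31.19 by 29.02 points. With the 43 subjects stated there, 28/43 = 65.1% and 60.21 − 31.19 = 29.02, so both figures reproduce. A group whose summary table shows these means is recognisable as the 2001 group.
- *Safeguards.* No section describes a second statistician, a firewall, or release of the forms only after a locked success analysis.

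**2. Where is the threshold?** Planned n is 43 (Sample Size). The success criteria require no less than 60%, and 0.60 × 43 = 25.8.

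- 25/43 = 58.1%, fails.
- 26/43 = 60.5%, passes.

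This reads the criterion as a point-estimate rule. No alpha is stated for the responder test. If P ≤ 60% were tested by exact binomial at one-sided 0.05 (an assumption), the pass mark would be 32/43 = 74.4% (tail probability 0.035; 31/43 gives 0.070).

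**3. How far could the imputation choice move the result?** Let x be observed responders, m missing endpoints and q the average imputed success probability. The pooled rate is (x + m·q)/43, which exceeds 60% when q > (25.8 − x)/m. The documents give no missing rate, so m is assumed.

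- m = 1, x = 25: q must exceed 0.80. The observed rate is 25/42 = 59.5%, so imputing near that rate still fails.
- m = 2, x = 25: q must exceed 0.40. Imputing near the observed rate, 25/41 = 61.0%, passes. A missing-not-at-random model with q below 0.40 fails.

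The outer bounds come from comparing all missing counted as failures with all counted as successes. The verdict then depends on imputation for x = 25 (m = 1), 24–25 (m = 2), 23–25 (m = 3) and 21–25 (m = 5). If the true rate is 65%, the binomial chance of landing there is 9.5%, 19.7%, 30.4% and 52.2%. If it is 60%, the chance is 12.4%, 24.9%, 37.1% and 59.2%. These are best-to-worst-case limits. A real imputation model moves the result less, as the m = 1 case shows.

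**4. How far could exclusions move the result?**

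- From 26/43, removing one responder gives 25/42 = 59.5%, so per-protocol fails.
- From 25/43, removing one non-responder also gives 25/42 = 59.5%, still a failure. Removing two gives 25/41 = 61.0%, but ITT has already failed and both must agree.

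Exclusions therefore cannot rescue a failed ITT result. They matter only when ITT passes, where the decision to exclude or keep a responder can decide whether the pass stands.

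**The case against.** The strongest reply is that the claim is limited to the success analysis and that the forms may be meant for the remaining analyses. The sentence about them sits in a records section, and the Blinding section says the coded data are de-identified. That would be workable if the forms came later or went to someone else, but the text says neither. It names the same role and gives the purpose as analysis of results.

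Several stronger conclusions that a reader might draw are not supported:

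- *That the open imputation method itself breaks the blind.* It does not. It is a separate gap in pre-specification, and it is what makes a failed blind matter.
- *That the analyst must know the current group to run the test.* Both groups' rates can be compared with 60% and decoded afterwards, and the two-sample t-test does not depend on the labels. Only interpretation needs the code.
- *That masking is the only control on bias.* The 30% responder definition, the 60% threshold, the 3-minute endpoint and the ITT/per-protocol agreement rule are all fixed in advance. Masking is the only *blinding*.
- *That subject identifiers expose the group.* "The Subject ID number will comprise the initials of the test site" investigator, but the coded dataset may not carry these identifiers, so this adds little.
- *That the choices will be made to suit the result.* The plan ties imputation to the amount and mechanism of missingness. The point is that nothing prevents it.

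Two further points stand. Baseline, treatment and endpoint follow one another in a single session, so few primary values may be missing; the 24- and 48-hour home forms feed only secondary descriptive analyses and per-protocol membership. And because subjects rate their own pain unblinded, masking the analyst gives limited protection even when it works.

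**Conclusion.** The contradiction is real: the plan claims a masking that its own data flow defeats, and the printed 2001 results weaken it further. It should be corrected, because it is the only blinding claimed and two decisions are left open behind it.

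The consequence is limited to results close to the threshold. A reader might infer that one imputed or excluded subject can decide the trial. That goes too far as a general statement. It assumes the point-estimate rule. With one missing endpoint and 25 of 42 observed responders, the imputed success probability would have to exceed 0.80. A single exclusion can only turn a pass into a fail. With two or more missing endpoints the choice of method can matter, but the documents give no missing rate from which to say how likely that is.

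The conclusion rests on reading the study statistician as one role throughout, as the text does, and on no unstated release order.

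**What to change.** 1. **Blinding claim.** Either delete the claim of a masked statistician from the Blinding section, or amend Confidentiality and Privacy so that existing staff not doing the analysis prepare the coded dataset and copies of the forms reach the statistician only after the success analysis is locked. A dedicated data manager is not needed. Under the second option the printed 2001 means still make the comparator recognisable, so masking would be partial and should be described as such.
2. **In either case**, change Handling of Missing Data and Populations Examined so that the imputation method, with a sensitivity analysis for data missing not at random, and a closed list of major deviations are fixed and dated before the statistician receives any outcome data.

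The cost is protocol and SAP wording, with no added subjects or procedures. The one small loss is that the imputation method can no longer be tuned to the missingness actually observed.
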